## Statistical Analysis Plan Template

Sponsor:	ProQR Therapeutics		
Protocol:	PQ-110-002		
Document Version No.:	1.0	Document Date:	04 JAN 2022

## Statistical Analysis Plan Template

Sponsor:	ProQR Therapeutics		
Protocol:	PQ-110-002		
Document Version No.:	1.0	Document Date:	04 JAN 2022

Descriptive statistics will be provided in summary tables, along with counts of missing values, characterized as either 'cannot grade' or 'not applicable'. A listing of all available data (quantitative values and qualitative replies of 'cannot grade' or 'not applicable' will also be provided.

### 4.7.7. **Prior and / or Concomitant Medications**

Medications administered to subjects during the study will be categorized as prior and/or concomitant medication. If usage of a medication stopped before the administration of the first dose of study treatment, it will be counted as a prior medication.

Two definitions of concomitant medications are required for this study:

A concomitant medication for the first treated eye will either have started prior to first dosing in the first treated eye and is defined as a 'prior and concomitant medication for the first treated eye', or will have started after first dosing in the first treated eye and is defined as a 'concomitant medication for the first treated eye'.

A concomitant medication for the treated and non-treated contralateral eye will either have started prior to first dosing in the contralateral eye and is defined as a 'prior and concomitant medication for the contralateral eye', or will have started after first dosing in the contralateral eye and is defined as a 'concomitant medication for the contralateral eye'.

Missing or partial start and end dates will be imputed as described in Section 4.2.9.4 before identifying whether to classify medication usage as prior or the two categories of concomitant medication.

Medications will be coded using the WHO Drug Global B3/C3-format March 1, 2021. Prior and concomitant medication usage by subjects in the Safety Population will be summarized. The summaries will be tabulated by treatment group, Anatomic Therapeutic Class (ATC) and preferred term, and will be presented separately for ocular and non-ocular concomitant medication usage.

## Statistical Analysis Plan Template

Sponsor:	ProQR Therapeutics		
Protocol:	PQ-110-002		
Document Version No.:	1.0	Document Date:	04 JAN 2022

The listing of prior and concomitant medication usage will identify whether the medication was ocular or non-ocular and, for ocular medication, whether the medication was a prior medication, a concomitant medication for the first treated eye starting prior to or after first dose of study treatment, or a concomitant medication for the contralateral eye starting prior to or after first dose of study treatment in the contralateral eye.

### 4.8. Efficacy Evaluation

Descriptive statistics of efficacy endpoints (Section 2.5.2) will be tabulated by treatment group, age category, and if appropriate, for treatment groups combined. The efficacy analysis will be conducted using the Efficacy Evaluable Population and Per Protocol Analysis Set. If Per Protocol Analysis Set is identical to the Efficacy Evaluable Analysis Population, the analysis results are only reported for Efficacy Evaluable Analysis Population.

#### 4.8.1. BCVA

The BCVA will be assessed using the BVRT and the ETDRS acuity test. The best BCVA reading (ie, smallest numerical value in logMAR) for the first treated eye (based on ETDRS/BVRT) at Screening is considered the baseline BCVA (see also Section 4.2.4).

BCVA is assessed using an ETDRS chart, or the BVRT (Bailey et al, 2012). ETDRS provides logMAR values using on-chart assessments (i.e., logMAR values  $< +1.7$ ). BVRT provides logMAR values based on off-chart assessments (i.e., logMAR values  $\geq +1.7$ ), which is meant for subjects who cannot read letters.

For subjects whose vision cannot be assessed with BVRT Single Tumbling E or Grating Acuity charts yielding logMAR values, the following BCVA measures can be provided based on BVRT: white field projection (WFP) and black and white discrimination (BWD). The measures of WFP and BWD represent more qualitative levels of vision as described by Bailey et al. 2012. For this study, imputed logMAR values will be used for WFP and BWD, as outlined in Table 2. For subjects with vision equal or worse than light perception (LP) data can be collected through the clinical practice assessment

## Statistical Analysis Plan Template

Sponsor:	ProQR Therapeutics		
Protocol:	PQ-110-002		
Document Version No.:	1.0	Document Date:	04 JAN 2022

---

When a BCVA assessment is performed, the assessment by ETDRS is completed first and, for 'off-chart' subjects (for whom ETDRS yields no results), will be followed by assessment of counting fingers (CF), hand movement (HM) and light perception (LP), performed as per clinical practice (not BRVT) and, subsequently, by BRVT assessment. Data based on ETDRS or BRVT will be the primary data used for analysis. If a logMAR value is available from both ETDRS and BRVT, only the ETDRS result will be used for analysis.

## Statistical Analysis Plan Template

Sponsor:	ProQR Therapeutics		
Protocol:	PQ-110-002		
Document Version No.:	1.0	Document Date:	04 JAN 2022

## Statistical Analysis Plan Template

Sponsor:	ProQR Therapeutics		
Protocol:	PQ-110-002		
Document Version No.:	1.0	Document Date:	04 JAN 2022

### 4.8.1.1. Descriptive Statistics and Listings

The mean observed value and change from baseline in logMAR values for BCVA based on ETDRS and BRVT will be summarized by treatment group, eye (first treated eye, treated contralateral eye, non-treated contralateral eye) and visit using continuous descriptive statistics on the logMAR scale for BCVA, using the Efficacy Evaluable Population. A second table with individual observed values and change from baseline over time will also be produced. In case subjects have individual BCVA responses based only on the clinical practice assessment, the corresponding logMAR values to be presented in the table will be based on both the Holladay equivalency table and the Lange equivalency table as described in Section 4.8.1.

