### 4.8.1.2. Responder Analysis for Treated Contralateral Eye

A responder analysis will be summarized on overall group and performed on all contralateral eyes treated in PQ-110-002 with the following definitions of responders:

- BCVA change from baseline for on-chart subjects (ie, BCVA < 1.7 logMAR based on ETDRS):
  - Equal or better than -0.2 logMAR, smaller values are better
  - Equal or better than -0.3 logMAR, smaller values are better
- BCVA change from baseline for off-chart subjects (ie, BCVA  $\geq$  1.7 logMAR based on BRVT/clinical practice assessment):
  - leading to a categorical change in VA category according to Holladay VA reference scale (Section 8):
    - From LP to HM or better, ie,
      - from logMAR 4 (clinical assessment) or logMAR 3.5 (BWD result from BRVT) to logMAR 3 (clinical assessment) or better (BRVT)
      - from logMAR 3.2 (WFP result from BRVT) to logMAR 2.9 or better (BRVT)
    - From HM to CF or better, ie,:
      - from logMAR 3 (if only clinical assessment result available) to logMAR 2 (if only clinical assessment result is available) or better (BRVT), OR:

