### 4.8.3. Full-Field Stimulus Threshold Testing (FST)

Full field stimulus testing captures threshold measurements for each stimulus (blue and red light).

Measurements with a Fail value of “0” are successful, and any measurements with a Fail value of “1” are unsuccessful. If the threshold value fails, the next successful value will be captured. FST thresholds will be measured by an independent reading center according to the schedule of events in section 2.4 and the Imaging Charter.

The mean FST values (i.e., light sensitivity) for each eye (first treated eye, treated and non-treated contralateral eye) will be summarized using continuous descriptive statistics by treatment group, eye and visit for each stimulus color, for all subjects in the Efficacy Evaluable Population. The FST values are the average of all FST stimulus sizes (in log cd/m^2) for the given eye at a given visit and stimulus color.

Descriptive statistics will be based on only successful thresholds ('acceptable data').

A responder analysis will be performed on the contralateral eyes treated in PQ-110-002 with the following definitions of responders:

- Blue FST change from baseline:
  - Equal or better than -0.7 log (cd/ m^2), smaller values are better
  - Equal or better than -0.5 log (cd/ m^2), smaller values are better
- Red FST change from baseline:

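### The mean BCVA table drops an eye that has only a clinical-practice acuity result, and the FST summaries have no visible rule for an eye that no longer detects the stimulus

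*SAP*

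**What the plan says.** **BCVA.** SAP 4.8.1 tests every eye first by ETDRS. An eye that is off the chart then has a clinical-practice check (counting fingers, hand movement, light perception), followed by the BRVT. "Data based on ETDRS or BRVT will be the primary data used for analysis". The two lowest BRVT levels, white field projection (WFP) and black-and-white discrimination (BWD), are given numbers: "For this study, imputed logMAR values will be used for WFP and BWD, as outlined in Table 2". Below that, "For subjects with vision equal or worse than light perception (LP) data can be collected through the clinical practice assessment".

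SAP 4.8.1.1 then defines two tables. The first holds group means: "The mean observed value and change from baseline in logMAR values for BCVA based on ETDRS and BRVT will be summarized by treatment group". The second holds individual values and changes. Directly after introducing the second, the SAP says: "In case subjects have individual BCVA responses based only on the clinical practice assessment, the corresponding logMAR values to be presented in the table" will use both the Holladay and the Lange equivalents. The natural reading is that clinical-only results go into the individual table and not into the means.

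**FST.** SAP 4.8.3 says: "Descriptive statistics will be based on only successful thresholds". If a threshold fails, the next successful one is taken. All failed and successful thresholds are listed.

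**Missing data.** SAP 4.2.9.2 imputes BCVA and FST only after withdrawal of consent or an unrelated death. If there is no measurement in a visit window, the closest measured value is used.

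**The concern.** In the narrow case of an eye that can no longer give a BRVT result, the value is absent from the mean because the outcome is bad. The mean change at that visit then describes only the eyes still good enough to test. The imputation triggers do not cover this case. FST has the same structure: an eye that truly fails to detect the stimulus has no successful threshold. It is then left out, or it takes a successful value from a later attempt or a neighbouring visit.

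The protocol's secondary objective is long-term and sustained efficacy, in a disease that it describes as slowly progressive. At most 11 subjects enrol, and SAP 4.2.2 splits the first treated eyes by their PQ-110-001 dose group. One eye can therefore change the sign or size of a reported mean.

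**Working it through.** The plan gives no figure to reproduce: it is descriptive and has no power calculation. The check is how far one eye moves a mean.

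**Inputs from SAP 4.8.1.2 (logMAR).** Holladay light perception (LP), clinical assessment: 4. BWD from the BRVT: 3.5. WFP from the BRVT: 3.2. Lange LP band: above 2.5 to 2.7; I use the upper end.

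**Assumed inputs.** Ten eyes; nine with the same change (-0.2 or 0); one eye starting at 2.0.

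**Formula.** Mean change = [9 × (change in the other eyes) + (code at visit - 2.0)] / 10. If the tenth eye is dropped, the mean is the change in the other nine.

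| Tenth eye falls to | In the planned mean? | Others at -0.2 | Others at 0 |
|---|---|---|---|
| Clinical-only LP, as planned | No | -0.20 | 0.00 |
| Same eye counted, Holladay 4.0 | – | (-1.8 + 2.0)/10 = +0.02 | +0.20 |
| Same eye counted, Lange 2.7 | – | (-1.8 + 0.7)/10 = -0.11 | +0.07 |
| BWD 3.5 | Yes | (-1.8 + 1.5)/10 = -0.03 | +0.15 |
| WFP 3.2 | Yes | (-1.8 + 1.2)/10 = -0.06 | +0.12 |

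The planned table therefore shows a large loss for an eye that falls to BWD (-0.03), and no loss at all for an eye that falls one step further (-0.20).

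**Group size.** With the others at -0.3 and a starting value of 2.5, dropping the eye gives -0.30. Counting it among 11 eyes gives (-3.0 + 1.5)/11 = -0.14 (Holladay) or (-3.0 + 0.2)/11 = -0.25 (Lange). Among 5 eyes it gives (-1.2 + 1.5)/5 = +0.06 or (-1.2 + 0.2)/5 = -0.20.

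**Opposite direction.** An eye that starts at clinical-only LP has no baseline in the mean table. If it improves to 2.9 on the BRVT, its Holladay change is 2.9 - 4.0 = -1.1. With nine others at -0.2, counting it gives (-1.8 - 1.1)/10 = -0.29, against -0.20 as planned. Here the exclusion works against the drug.

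**Choice of code.** A fall from BWD to clinical-only LP is 4.0 - 3.5 = +0.5 on Holladay but 2.7 - 3.5 = -0.8 on Lange, an apparent gain. Putting either code into the mean would not be a clean remedy.

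**FST.** The documents do not say how many failures are true non-detections. Assume eleven eyes, ten at -0.7 and one with no threshold. Dropped, the mean is -0.70. Counted at an assumed change of 0 to +2 log, it is (-7.0 + 0)/11 = -0.64 to (-7.0 + 2)/11 = -0.45. For a responder rate with five responders, it is 5/10 = 50% if dropped and 5/11 = 45% if counted as a non-responder.

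**The case against.** A reader might infer that any eye too poor to test disappears from the analysis. The documents do not support that:

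- Off-chart eyes go on to the BRVT, and the responder rules in SAP 4.8.1.2 place BWD and WFP within the LP-to-hand-movement step. Many eyes at LP level therefore stay in the mean as large losses.
- A clinical-only eye leaves the mean table only. It keeps its place in the individual table and the listing, and in the off-chart responder analysis (treated contralateral eyes) or preservation analysis (first treated eyes).
- SAP 4.2.1 reports the number of subjects with each continuous efficacy summary, so a lost eye shows as a smaller n.
- Keeping clinical codes out of a mean is defensible when the two scales disagree as much as shown above.
- An FST fail is defined only as unsuccessful. Nothing equates it with non-detection, and it may reflect test quality.

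All of this stands, and it narrows the point. It does not remove it. A smaller n does not say why the eye is missing, and the individual table does not correct the group mean. No visible rule classifies an eye with no successful FST threshold in the responder or preservation tables. The SAP itself expects clinical-only results: it gives them baseline categories in 4.6 and branches in 4.8.1.2.

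Part of SAP 4.8.1, including Table 2 and the equivalency tables, is not visible. If a rule there, or a wider meaning of the table named in 4.8.1.1, brings clinical-only values into the means, the BCVA half falls away.

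**Conclusion.** The point holds in a limited form. As worded, the mean BCVA table omits an eye with only a clinical-practice result, and the FST summaries omit or substitute an eye with no successful threshold. In the ten-eye illustration, the BCVA omission moves the mean by 0.22 (Holladay) or 0.09 (Lange) logMAR. The inputs are assumed, and a fall from 2.0 to clinical-only LP is a severe case.

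A reader might also infer that the bias always favours the drug. It does so when treated eyes deteriorate out of the table, but it can go the other way for eyes that start at clinical-only LP and improve. No FST effect can be established without the reasons for failure. Safety is the primary objective and no inferential analysis is planned, so this is an inexpensive improvement to a secondary summary and not a flaw in the trial. Confidence is moderate because of the text that is not visible.

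**What to change.** **SAP 4.8.1.1.** For each eye group and visit, report the number of eyes tested that have no ETDRS or BRVT value. Add one sensitivity summary that includes them. This can be a median change in which a fall to clinical-only LP or worse takes the worst rank, so that no chosen logMAR code drives it. It can instead be a baseline-to-visit shift table in the SAP's own categories (LP, hand movement, counting fingers, on-chart). If a rule already exists in 4.8.1, cite it here.

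**SAP 4.8.3.** For each visit, report the number of eyes with no successful threshold, split into technical failure and non-detection. Count non-detection as a non-responder and as not preserved, and do not drop it or replace it with a value from another visit.

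**Cost.** SAP wording and a few table rows from data already collected. SAP 4.7.6 already counts ungradable OCT values in this way, and 4.2.9 already captures reasons for missing data. FST failures must be classified by reason, and the acuity summary may look less favourable.

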## Statistical Analysis Plan Template

Sponsor:	ProQR Therapeutics		
Protocol:	PQ-110-002		
Document Version No.:	1.0	Document Date:	04 JAN 2022

Descriptive summaries of BCVA for the subpopulations of subjects defined in Section 4.2.7 will also be provided.

A subject listing of visual acuity (BCVA), including all available data will be produced for the Efficacy Evaluable Population, including both the actual value and change from baseline at post-baseline time points.

### 4.8.1.2. Responder Analysis for Treated Contralateral Eye

A responder analysis will be summarized on overall group and performed on all contralateral eyes treated in PQ-110-002 with the following definitions of responders:

- BCVA change from baseline for on-chart subjects (ie, BCVA < 1.7 logMAR based on ETDRS):
  - Equal or better than -0.2 logMAR, smaller values are better
  - Equal or better than -0.3 logMAR, smaller values are better
- BCVA change from baseline for off-chart subjects (ie, BCVA  $\geq$  1.7 logMAR based on BRVT/clinical practice assessment):
  - leading to a categorical change in VA category according to Holladay VA reference scale (Section 8):
    - From LP to HM or better, ie,
      - from logMAR 4 (clinical assessment) or logMAR 3.5 (BWD result from BRVT) to logMAR 3 (clinical assessment) or better (BRVT)
      - from logMAR 3.2 (WFP result from BRVT) to logMAR 2.9 or better (BRVT)
    - From HM to CF or better, ie,:
      - from logMAR 3 (if only clinical assessment result available) to logMAR 2 (if only clinical assessment result is available) or better (BRVT), OR:

## Statistical Analysis Plan Template

Sponsor:	ProQR Therapeutics		
Protocol:	PQ-110-002		
Document Version No.:	1.0	Document Date:	04 JAN 2022

- from logMAR 3 (if only clinical assessment result available) to logMAR 1.7 - 2 or better (BRVT), OR:
  - from logMAR >2 – 2.9 (based on BRVT) to logMAR 1.7 - 2 or better (based on BRVT), AND the BCVA change from baseline is equal or better than -0.3 logMAR (ie,  $\leq$  -0.3 logMAR)
- From CF to on-chart, ie.:
  - from logMAR 2 (if only clinical assessment result available) to a logMAR value of < 1.7 based on ETDRS
  - from logMAR 1.7 - 2 (based on BRVT) to a logMAR value of < 1.7 based on ETDRS AND the BCVA change from baseline is equal or better than -0.3 logMAR (ie,  $\leq$  -0.3 logMAR)
- leading to a change in VA category according to Lange VA reference scale (Section 9)
  - From LP to HM or better, ie:
    - from logMAR >2.5 - 2.7 (based on BRVT/clinical assessment) to >2 - 2.5 (based on BRVT/clinical assessment) AND the BCVA change from baseline is equal or better than -0.3 logMAR (ie,  $\leq$  -0.3 logMAR)
  - From HM to CF, ie.:
    - from logMAR 2.3 (if only clinical assessment result available) to logMAR 1.7 - 2 or better (based on BRVT), OR:
      - from logMAR >2 - 2.5 (based on BRVT) to logMAR 1.7 - 2 or better (based on BRVT), AND the BCVA change from baseline is equal or better than -0.3 logMAR (ie,  $\leq$  -0.3 logMAR)
  - From CF to on-chart, ie.:

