## Statistical Analysis Plan Template

Sponsor:	ProQR Therapeutics		
Protocol:	PQ-110-002		
Document Version No.:	1.0	Document Date:	04 JAN 2022

- from logMAR 2 (if only clinical assessment result available) to a logMAR value of < 1.7 based on ETDRS
- from logMAR 1.7-2 (based on BRT) to a logMAR value of < 1.7 based on ETDRS AND the BCVA change from baseline is equal or better than -0.3 logMAR (ie,  $\leq$  -0.3 logMAR)

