## Statistical Analysis Plan Template

Sponsor:	ProQR Therapeutics		
Protocol:	PQ-110-002		
Document Version No.:	1.0	Document Date:	04 JAN 2022

- BCVA change from baseline for off-chart subjects (ie, BCVA  $\geq 1.7$  logMAR based on BVRT/clinical practice assessment): leading to a categorical change in VA category according to Holladay VA reference scale (Section 8) or Lange VA reference scale (Section 9)
  - Among the subjects that are responders at month 12 to the responder criterion defined in the section 4.8.1.2, the same rule used for on-chart subjects will be performed.

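### The numeric Lange rule for LP eyes counts a move into the HM band but not a larger gain, contradicting its own heading, and gives BRVT values above 2.7 logMAR no starting category

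*SAP*

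**What the plan says.** SAP 4.8.1.2 lists off-chart responder definitions under two reference scales. The Lange steps are:

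- **LP step.** The heading is "From LP to HM or better, ie". The numeric definition is "from logMAR >2.5 - 2.7 (based on BRVT/clinical assessment) to >2 - 2.5 (based on BRVT/clinical assessment"), with the further condition "AND the BCVA change from baseline is equal or better than -0.3 logMAR".
- **HM step.** Either "from logMAR 2.3 (if only clinical assessment result available) to logMAR 1.7 - 2 or better (based on BRVT), OR", or "from logMAR >2 - 2.5 (based on BRVT) to logMAR 1.7 - 2 or better (based on BRVT") with the same -0.3 condition.
- **Counting fingers (CF) step.** From a clinical value of 2, or "from logMAR 1.7-2 (based on BRT) to a logMAR value of < 1.7 based on ETDRS" with the -0.3 condition.

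The Holladay steps in the same section have open end points. One LP step reads "from logMAR 3.2 (WFP result from BRVT) to logMAR 2.9 or better (BRVT"). The BRVT part of the Holladay HM step accepts starting values above 2 and up to 2.9, with an end point of 1.7 to 2 or better.

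For off-chart first treated eyes, SAP 4.8.1.3 reuses the criterion: "Among the subjects that are responders at month 12 to the responder criterion defined in the section 4.8.1.2". It names the Holladay scale or the Lange scale.

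**The concern.** A responder rule should not fail an eye for improving more. The Lange LP step is closed at its better end, and no other Lange step picks up an eye that starts above 2.5 and finishes at 2.0 or better. The numbers therefore disagree with the heading they are meant to spell out.

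The start band also stops at 2.7, although the section itself contemplates numeric BRVT results up to 2.9.

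At stake is the Lange off-chart responder rate for treated contralateral eyes. An eye wrongly left out as a responder could also drop out of the month 12 responder set used for off-chart vision preservation in first treated eyes.

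**Working it through.** The SAP states no figure to reproduce here, so the check applies the printed rules to pairs of baseline and follow-up values.

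**Inputs (SAP 4.8.1.2, logMAR, smaller is better)**

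- Lange LP: start >2.5 to 2.7, end >2 to 2.5, change <= -0.3.
- Lange HM (BRVT): start >2 to 2.5, end <= 2, change <= -0.3.
- Lange CF (BRVT): start 1.7 to 2, end <1.7 on ETDRS, change <= -0.3.
- Holladay HM (BRVT): start >2 to 2.9, end <= 2, change <= -0.3.
- Maximum sample: 11 subjects (protocol synopsis), so at most 11 treated contralateral eyes.

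Assumption: an end point stated as a band or better includes on-chart ETDRS values.

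**Individual pairs (change = follow-up minus baseline)**

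| Baseline to follow-up | Change | Lange as printed | Holladay as printed |
|---|---|---|---|
| 2.6 to 2.3 | -0.3 | responder | non-responder |
| 2.7 to 2.3 | -0.4 | responder | non-responder |
| 2.7 to 2.1 | -0.6 | responder | non-responder |
| 2.7 to 2.0 | -0.7 | non-responder | responder |
| 2.7 to 1.9 | -0.8 | non-responder | responder |
| 2.7 to 1.6 (on-chart) | -1.1 | non-responder | responder |
| 2.9 to 2.3 | -0.6 | non-responder | non-responder |
| 2.9 to 1.9 | -1.0 | non-responder | responder |

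From a baseline of 2.7, response under Lange switches off once the eye reaches 2.0. From 2.9 it is never available.

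**Extent on a grid.** Follow-up values run from 1.0 to 2.5 in steps of 0.1, keeping only pairs with change <= -0.3. The grid is an assumption, and the counts are pairs of values, not expected patient proportions.

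- Starts of 2.6 and 2.7: 14 + 15 = 29 qualifying pairs. Lange as printed accepts 3 + 4 = 7. With the end point read as 2.5 or better, it accepts 29.
- Starts of 2.8 and 2.9: 16 + 16 = 32 qualifying pairs. Lange as printed accepts 0. Holladay accepts 11 + 11 = 22, so 32 - 22 = 10 respond on neither scale. These are the moves into the >2 to 2.5 band.

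**Size.** One eye in 11 is 1/11 = 9.1 percentage points. The step is larger if the denominator is off-chart eyes only; the documents do not give that number.

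**The case against.** The strongest reply is that the heading already says HM or better, and CF is better than HM. On that view the SAP does not plainly score a gain from LP to CF as failure; its words and its numbers disagree. That is fair, and it is the right description of the defect. It does not remove the problem, because the numeric line is offered as the meaning of the heading and is what would be programmed.

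A reader might infer that eyes recorded as white field projection (WFP) or black and white discrimination (BWD) can never respond under Lange. The documents do not establish this. The values 3.2 and 3.5 appear in the Holladay steps. SAP 4.8.1 places the imputed values in Table 2, and neither that table nor the Lange scale cited as Section 9 is shown. The scales already code clinical HM differently (3 under Holladay, 2.3 under Lange), so different WFP and BWD values for Lange are possible.

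A reader might also attribute any gap between Lange and Holladay rates to this wording. That goes too far: the HM start bands differ by design, >2 to 2.9 against >2 to 2.5, so the rates can differ anyway.

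Finally, SAP 4.8.1.3 joins the two scales with an or. If response on either scale suffices, Holladay captures every gain from 2.6 or 2.7 to 2.0 or better that Lange misses. Moves from above 2.7 up to 2.9 into the >2 to 2.5 band would still be missed. The SAP does not say how the two scales are combined in 4.8.1.2.

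**Conclusion.** The Lange LP step is wrong as written. Its numeric end point contradicts its heading, is out of line with the open end points of the Lange HM step and the Holladay steps, and makes response non-monotone in improvement. Numeric BRVT values above 2.7 and up to 2.9 have no Lange start category. Whether WFP and BWD eyes are also excluded cannot be judged without Table 2 and Section 9.

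The consequence is limited. The analysis is secondary and descriptive, the primary endpoints are adverse events, and individual BCVA values and changes are tabulated and listed (SAP 4.8.1.1), so a large gain would stay visible. No affected eye is shown to exist. The reach is the Lange off-chart responder rate, at 9.1 points or more per eye, and possibly the off-chart preservation denominator. These conclusions assume that the numbers, not the heading, are coded and that Lange response is reported on its own; the effect shrinks if either scale counts.

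**What to change.** In SAP 4.8.1.2, change the numeric end point of the Lange LP step to logMAR 2.5 or better (BRVT, clinical assessment or ETDRS), keeping the condition of a change of -0.3 logMAR or better.

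Extend the Lange start bands so that BRVT values above 2.7 belong to a stated category. Place WFP and BWD according to the values that Table 2 and Section 9 give them for the Lange analysis. The choice of category should be explicit because it matters: on the grid above, starts of 2.8 and 2.9 give 32 of 32 qualifying pairs as responders if placed in LP with the corrected end point, and 22 of 32 if placed in HM.

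Also state in 4.8.1.2 and 4.8.1.3 whether Holladay and Lange response are reported separately or combined.

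The cost is SAP wording and the matching program specification. No new data are needed.
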